9.4 STATISTICAL ANALYSES PLAN

Preliminary analyses will include generating descriptive statistics for demographic variables, as well as baseline characteristics and follow-up measures. This includes means and standard deviations for continuous variables, and frequencies and percentages for categorical variables. Ranges will also be examined for outliers and to ensure data integrity. Demographics and baseline characteristics will also be described separately by randomized group.

We hypothesize that participants receiving the OA-PCP will have greater improvement in MVPA compared with the attention control group at 6 and 12 months. To determine the effects of the intervention on MVPA, repeated measures will be analyzed using linear mixed effects models, with clinic included as a random effect, to estimate mean change and 95% confidence intervals in MVPA from baseline to 6-month and 12-month time points. This model will account for intra-person clustering for the repeated measures, including a group x time effect. We will use the same modeling strategy for continuous secondary and exploratory outcomes. An advantage of this modeling approach is that it uses all available data; participants are not dropped if they miss a time point. This approach will reduce the overall amount of missing data and could eliminate the need for imputation of missing repeated outcomes¹⁰⁰. However, if we find that missing data are related to measured patient factors (i.e., missing not at random [MNAR]), we will carry out sensitivity analyses by imputing missing values under the MNAR scenario and examining the results. The SAS procedure PROC MI has several options for using multiple imputation in sensitivity analyses based on pattern-mixture models for MNAR data, which model the distribution of a response as the mixture of a distribution of the observed responses and a distribution of the missing responses¹⁰¹. Multiple imputation has the advantage of providing a framework for incorporating information from these variables, while preserving a parsimonious main treatment effect model^{102, 103}. Analyses will be conducted on an intent-to-treat basis and carried out using SAS 9.4 (SAS Institute Inc., Cary, NC). Tests will be two-sided and considered significant at the 0.05 level.

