Exploration of Mediators. We are interested in understanding the degree to which various facets of the OA-PCP contribute to improvements in PA and other outcomes. Because the mediating variables of interest (described above) pertain only to the OA-PCP group, our strategy will differ from a traditional mediation analysis approach in the context of a clinical trial. Specifically, we will use linear regression models to assess associations between potential mediating variables and outcomes among individuals in the OA-PCP group. Each potential mediator will be assessed individually, then we will fit a multivariable model including all variables with bivariate associations of $p \leq 0.1$. Analyses will be performed for both 6 and 12 month outcomes.

Exploration of Moderators. We will explore potential differential treatment effects based on participant characteristics, particularly gender, age and baseline PAVS score. The latter is of interest to help inform the inclusion criterion for a larger trial; if individuals with higher baseline PA (though not meeting DHHS recommendations) make little additional improvement in PA, we may focus on individuals with lower PA levels at screening. For assessment of differential treatment effects, we will conduct stratified analyses based on participant characteristics (e.g., men / women, age categories by decade, quartiles of baseline PAVS scores). We propose this strategy because the study is not powered to detect interactions between treatment group and participant characteristics. We will also use multivariable logistic regression^{104,105} and recursive partitioning (RP)^{106,107} to explore multidimensional subgroups that exhibit heterogeneous treatment effects; these analyses will focus on our a priori characteristics of interest but also explore additional variables.

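### Moderators are examined only stratum by stratum: no interaction or between-stratum estimate with a CI is planned, although the PAVS result may shape the larger trial's inclusion criterion

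*Combined protocol and SAP*

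**What the plan says.** The paragraph on moderators in section 9.4 names sex, age and baseline PAVS score as the characteristics of main interest. The method is stratification: "we will conduct stratified analyses based on participant characteristics (e.g., men / women, age categories by decade, quartiles of baseline PAVS scores". The reason given is "We propose this strategy because the study is not powered to detect interactions between treatment group and participant characteristics".

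The PAVS analysis has a stated use: "The latter is of interest to help inform the inclusion criterion for a larger trial". If more active participants "make little additional improvement in PA, we may focus on individuals with lower PA levels at screening".

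Two further methods are listed: "We will also use multivariable logistic regression" and recursive partitioning, both intended "to explore multidimensional subgroups that exhibit heterogeneous treatment effects; these analyses will focus on our a priori characteristics of interest".

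The main model, earlier in section 9.4, is a linear mixed model used "to estimate mean change and 95% confidence intervals in MVPA from baseline to 6-month and 12-month time points". On its structure the plan says: "This model will account for intra-person clustering for the repeated measures, including a group x time effect". No term linking treatment to a moderator is named there or in the moderator paragraph. Section 8.1 lists the moderators but leaves their analysis to section 9.

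**The concern.** Low power for interactions is a reason for caution about interactions. It is not a reason to replace them with separate analyses. Whether the effect differs by baseline activity is a question about the difference between strata. Analysing each stratum alone leaves that difference just as imprecise and also leaves it unreported.

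The other two methods do not clearly fill the gap. Neither is described as giving a treatment-by-PAVS estimate with its uncertainty, and no binary outcome is defined for the logistic model. A reader could derive a contrast from stratum estimates and their standard errors. The plan commits to 95% CIs for the main MVPA model but does not say that either will be reported for the moderators.

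What is at stake is a design choice for the next trial. If the top PAVS quartile happens to show a small estimate, that could be read as evidence that more active patients do not benefit, when the data are compatible with no difference at all.

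**Working it through.** **Inputs**
- N = 240, 120 per arm; 10% attrition; expected effect 0.3–0.7 SD; power stated for 0.38 SD (section 9.2).
- Two-sided 5% tests; PAVS quartiles (section 9.4).
- Valid follow-up accelerometer data in 86% of Aim 2 participants (section 8.1).
- Assumptions not in the documents: equal quartiles, 1:1 allocation within each, independent strata, outcome in SD units, normal approximation, and no gain from baseline adjustment unless stated.

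**The plan's own figure**

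120 × 0.90 = 108 per arm; SE = √(2/108) = 0.136. Power at 0.38 = Φ(0.38/0.136 − 1.96) = 79.7%. The stated figure of about 80% reproduces.

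**Precision within a PAVS quartile**

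216/8 = 27 per arm. SE = √(2/27) = 0.272; 95% CI half-width = 1.96 × 0.272 = 0.533 SD. Power within one quartile at 0.38 SD is 29%.

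**Chance of a misleadingly small top-quartile estimate**

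Suppose the true effect d is the same in all quartiles. Then P(top estimate < c) = Φ((c − d)/SE). The cut-off c is illustrative, since the plan states none.

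| | d = 0.3 | 0.38 | 0.5 | 0.7 |
|---|---|---|---|---|
| c = 0.1, SE 0.272 | 23.1% | 15.2% | 7.1% | 1.4% |
| c = 0, SE 0.272 | 13.5% | 8.1% | 3.3% | 0.5% |
| c = 0.1, SE reduced by 20% (assumed gain from baseline data) | 17.9% | 9.9% | 3.3% | 0.3% |
| c = 0.1, 86% with valid data: 240 × 0.86/8 = 25.8 per arm, SE 0.278 | 23.6% | 15.7% | 7.5% | 1.6% |

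**Precision of the missing contrast**
- Top quartile versus the rest: SE = √(2/27 + 2/81) = 0.314; half-width 1.96 × 0.314 = 0.616 SD. Power for a 0.38 SD difference is 22.7%; 80% power needs 2.80 × 0.314 = 0.88 SD.
- Two equal strata, 54 per arm each: SE = √(4/54) = 0.272; half-width 0.533 SD.

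**What a strict filter would do**

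Suppose the larger trial were narrowed only if the top quartile fell below 0.1 SD and the CI for top versus rest also excluded zero (numerical integration):

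| Truth | d = 0.38 | 0.5 | 0.7 |
|---|---|---|---|
| Same effect d everywhere: narrowing is wrong, no filter | 15.2% | 7.1% | 1.4% |
| Same, with filter | 2.4% | 2.1% | 0.9% |
| Top quartile 0, rest d: narrowing is right, no filter | 64.3% | 64.3% | 64.3% |
| Same, with filter | 22.5% | 34.9% | 54.4% |

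The filter prevents most false narrowing at 0.38 and 0.5 SD, but at all three effect sizes it gives up more correct narrowing than it prevents of the false kind.

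**The case against.** The strongest reply is that the inclusion decision turns largely on how much the more active group gains. That is a within-stratum quantity, and its own CI of about ±0.53 SD already shows how little is known. A contrast can be clearly non-zero while that group still benefits. This stands in part, and it is why both estimates should be reported.

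Second, the plan states no decision rule. It speaks only of helping to inform the criterion and of a possible focus, so reading the result from a point estimate is a supposition and the 0.1 SD cut-off is invented. This is true; the percentages illustrate the hazard and do not predict what the team will do. They also count trials with an inconclusive main result. If overall significance were required as well (again an assumption, not a rule in the plan), the joint probability at 0.3, 0.38, 0.5 and 0.7 SD would be about 7%, 8%, 6% and 1.4%.

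Third, a short exploratory paragraph need not set out reporting format, and its silence is not a plan to give bare point estimates. That is fair as far as stratum CIs go. It does not answer the absence of any contrast, because the plan expressly chooses stratification in place of interactions.

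Fourth, no gain has been quantified for weighing both estimates, and three moderators at two follow-up times add at least six imprecise interaction estimates. Both points stand. They argue for labelling the estimates exploratory, not for leaving them out.

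**Conclusion.** The concern holds as a point to consider. The plan sets out to assess differential effects but specifies no estimate of a difference in effect and no interval for one; the stated reason, low interaction power, does not justify the omission.

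The risk of reading chance variation as heterogeneity is material at the lower end of the protocol's expected range (23% at 0.3 SD, 15% at 0.38 SD) and small at the upper end (1.4% at 0.7 SD), on the assumptions and illustrative cut-off given above. The PAVS distribution is not given; unequal or tied quartiles would change these figures.

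The textual gap is certain. Its consequence depends on how the team uses the result. The analysis is openly exploratory, the lack of power is disclosed, the link to the inclusion criterion concerns PAVS only and is conditional, and H1 and H2 are untouched.

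**What to change.** In section 9.4:
- Add exploratory treatment × time × moderator terms for sex, age and PAVS to the mixed model already planned.
- Preferably keep age and PAVS continuous, with a linearity check or an ordered-quartile trend. Section 5.1 caps PAVS below 150 minutes per week, and scores may be tied.
- Report each interaction estimate with its 95% CI beside the stratum effects with theirs, all labelled exploratory.
- State that any change to the larger trial's inclusion criterion will weigh both and will not rest on within-stratum point estimates or significance alone.
- Do not require the interaction CI to exclude zero.

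The cost is some SAP wording and a few model terms, with no new data. The added intervals will be wide and the trial will remain underpowered for interactions. A linear PAVS term brings a shape assumption that quartiles avoid. What is gained is that designers of the larger trial can see how uncertain any apparent difference is.

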10 SUPPORTING DOCUMENTATION AND OPERATIONAL CONSIDERATIONS

10.1 REGULATORY, ETHICAL, AND STUDY OVERSIGHT CONSIDERATIONS

10.1.1 INFORMED CONSENT PROCESS

10.1.1.1 CONSENT AND OTHER INFORMATIONAL DOCUMENTS PROVIDED TO PARTICIPANTS

Consent forms describing in detail the study intervention, study procedures, and risks will be given to the participant and written documentation of informed consent will be completed prior to starting the study intervention. The following consent materials are submitted with this protocol: Adult Consent Form.

10.1.1.2 CONSENT PROCEDURES AND DOCUMENTATION

Once a potential participant meets the medical record and telephone screening criteria for eligibility, and is interested in participating, the study team member will begin the verbal consenting process by phone. If the participant does not have time to complete the verbal consent, the study team member will arrange a date and time to call the participant back. No other study activities will occur until this process is completed.

We will use a UNC IRB approved consent form / script with included language that satisfies the HIPAA requirements and outlines the protection of health information utilized in the study.

Verbal informed consent and HIPAA authorization will be obtained by a trained study team member. The study team member will read the IRB approved verbal consent script and HIPAA authorization to the potential participant and provide an opportunity for him/her to ask any questions that they may have about the research study. We anticipate this process to take approximately 20 minutes, but this time will not be limited should a participant have additional questions or concerns regarding the study. During this phase of the consent process, it will be stressed that the participant is not obligated to participate in the study, that participation is completely voluntary, and that he/she may withdrawal from the study at any time without penalty. Also, potential risks from participating in the study will be outlined in the consent form, as are the measures taken to protect against study specific risks. Once the information in the consent form and HIPAA authorization is fully reviewed and understood by the individual, he/she will be asked to decide at that time if they would like to voluntarily participate in the research study. If the individual does choose to participate in the study, the study team member will document in REDCap the date verbal consent and the date HIPAA authorization is collected. No activities will commence until verbal consent and HIPAA authorization are collected. Each enrolled participant will then be mailed a copy of the consent form and HIPAA authorization to keep for their records.

If after review of the consent form, the potential participant is not sure they would like to participate in the study at this time, they may choose to consider the study further, and then contact the study team if they decide later that they would like to participate.

Participants will only be included if they have capacity to give legally effective consent. Additionally, this study will only recruit participants whom are English speakers.

10.1.2 STUDY DISCONTINUATION AND CLOSURE

This study may be temporarily suspended or prematurely terminated if there is sufficient reasonable cause. Written notification, documenting the reason for study suspension or termination, will be provided by the suspending or terminating party to study participants, investigator, funding agency, and regulatory authorities. If the study is prematurely terminated or suspended, the PI will promptly inform study participants, the IRB, and sponsor/funding agency and will provide the reason(s) for the termination or suspension. Study participants will be contacted, as applicable, and be informed of changes to study visit schedule.

Circumstances that may warrant termination or suspension include, but are not limited to:

- Determination of unexpected, significant, or unacceptable risk to participants

- Demonstration of efficacy that would warrant stopping
- Insufficient compliance to protocol requirements
- Data that are not sufficiently complete and/or evaluable
- Determination that the primary endpoint has been met
- Determination of futility

The study may resume once concerns about safety, protocol compliance, and data quality are addressed, and satisfy the funding agency, sponsor, IRB or other relevant regulatory or oversight bodies (OHRP, SO).

10.1.3 CONFIDENTIALITY AND PRIVACY

Participant confidentiality and privacy is strictly held in trust by the participating investigators, their staff, the safety and oversight monitor(s), and the sponsor(s) and funding agency. This confidentiality is extended to the data being collected as part of this study. Data that could be used to identify a specific study participant will be held in strict confidence within the research team. No personally-identifiable information from the study will be released to any unauthorized third party without prior written approval of the sponsor/funding agency.

All research activities will be conducted in as private a setting as possible.

The study monitor, other authorized representatives of the sponsor or funding agency, representatives of the IRB, regulatory agencies or representatives from companies or organizations supplying the product, may inspect all documents and records required to be maintained by the investigator, including but not limited to, medical records (office, clinic, or hospital) and pharmacy records for the participants in this study.

The study participant's contact information will be securely stored on a secure study database for internal use during the study. At the end of the study, all records will continue to be kept in a secure location for as long a period as dictated by the reviewing IRB, Institutional policies, or sponsor/funding agency requirements.

Study participant research data, which is for purposes of statistical analysis and scientific reporting, will be stored on a secure UNC server. The study data entry and study management systems used by research staff will be secured and password protected. At the end of the study, all study databases will be de-identified and archived on a secure UNC server.

Measures Taken to Ensure Confidentiality of Data Shared per the NIH Data Sharing Policies

It is NIH policy that the results and accomplishments of the activities that it funds should be made available to the public (see <https://grants.nih.gov/policy/sharing.htm>). The PI will ensure all mechanisms used to share data will include proper plans and safeguards for the protection of privacy, confidentiality, and security for data dissemination and reuse (e.g., all data will be thoroughly de-identified and will not be traceable to a specific study participant). Plans for archiving and long-term preservation of the data will be implemented, as appropriate.

Certificate of Confidentiality

To further protect the privacy of study participants, the Secretary, Health and Human Services (HHS), has issued a Certificate of Confidentiality (CoC) to all researchers engaged in biomedical, behavioral, clinical or other human subjects research funded wholly or in part by the federal government. Recipients of NIH funding for human subjects research are required to protect identifiable research information from forced disclosure per

the terms of the NIH Policy (see <https://humansubjects.nih.gov/coc/index>). As set forth in [45 CFR Part 75.303\(a\)](#) and [NIHGPS Chapter 8.3](#), recipients conducting NIH-supported research covered by this Policy are required to establish and maintain effective internal controls (e.g., policies and procedures) that provide reasonable assurance that the award is managed in compliance with Federal statutes, regulations, and the terms and conditions of award. It is the NIH policy that investigators and others who have access to research records will not disclose identifying information except when the participant consents or in certain instances when federal, state, or local law or regulation requires disclosure. NIH expects investigators to inform research participants of the protections and the limits to protections provided by a Certificate issued by this Policy.

10.1.4 FUTURE USE OF STORED DATA

Data collected for this study will be analyzed and stored on a secure UNC server. After the study is completed, the de-identified data will be made available to other researchers, available by request to the PI. Investigators requesting study data must adhere to regulatory requirements for data use (e.g., IRB approvals, data use agreements). No biological samples are collected for this study.

10.1.6 SAFETY OVERSIGHT

Safety oversight will be under the direction of the NIA appointed SO. The SO will be independent from the study conduct and free of conflict of interest. On a biannual basis, the PI will provide to the SO a study summary, a report of all AEs, and any problems or issues that have been identified.

10.1.7 CLINICAL MONITORING

Since this is a single site study there will not be site visits conducted by the PI or co-investigators. However, we will monitor the fidelity of intervention delivery as described above.

10.1.8 QUALITY ASSURANCE AND QUALITY CONTROL

Quality control (QC) procedures will be implemented as follows:

Informed consent --- During the consenting process, the study team member will review the completed consent document to ensure the participant has signed and dated the consent form accurately prior to completing any other study activities.

Source documents and the electronic data --- Data from study measures will be entered directly into the study database. If the study database is not accessible, data will be captured on a source document and will ultimately be entered into the study database. To ensure accuracy site staff will compare a representative sample of source data against the database.

Intervention Fidelity — Consistent delivery of the study interventions will be monitored throughout the intervention phase of the study. Procedures for ensuring fidelity of intervention delivery are described in **Section 6.2**

Protocol Deviations – The study team will review protocol deviations on an ongoing basis and will implement corrective actions when the quantity or nature of deviations are deemed to be at a level of concern.

Should independent monitoring become necessary, the PI will provide direct access to all trial related sites, source data/documents, and reports for the purpose of monitoring and auditing by the sponsor/funding agency, and inspection by local and regulatory authorities.

10.1.9 DATA HANDLING AND RECORD KEEPING

10.1.9.1 DATA COLLECTION AND MANAGEMENT RESPONSIBILITIES

Study data will be stored on a secure UNC server in a folder accessible only to IRB-approved study team members. We will use REDCap to store all patient information and dispositions, responses to screening and outcome assessments. REDCap is a secure web application supported at UNC that can be used to build and manage case report forms, surveys, and other data capture mechanisms.

10.1.9.2 STUDY RECORDS RETENTION

Research study records will be maintained for no less than 6 years following the completion of the study, after which time personal identifying information will be removed. Research information in a subject's medical record will be kept indefinitely. No records will be destroyed without the written consent of the sponsor/funding agency, if applicable. It is the responsibility of the sponsor/funding agency to inform the investigator when these documents no longer need to be retained.

